	
 • Immunogenicity: Immune response to the CS and HBs antigens (immunogenicity subset) 
 – Anti-CS antibody concentrations and seropositivity measured before Dose 1, one month post-Dose 2 (group Fx017-mFxD only), before and one month post-Dose 3, before and one month after Dose 4, before and one month after each yearly dose and at study end (Month 50). – Anti-HBs antibody concentrations and seropositivity measured before Dose 1, one month post-Dose 2 (group Fx017-mFxD only), before and one month post-Dose 3, before and one month after Dose 4, before and one month after each yearly dose and at study end (Month 50).
	
Amended 14 November 2019
 
 • Safety 
 – The occurrence of SAEs (all, fatal and related) during the whole study period according to the MedDRA classification. – The occurrence of AEs and SAEs leading to withdrawal from further vaccination from Dose 1 (Day 0) up to Month 50, according to the MedDRA classification. – The occurrence of severe malaria cases and cerebral malaria cases during the whole study period. – The occurrence of pIMDs from Day 0 up to Month 50, according to the MedDRA classification.

- The occurrence of meningitis from Day 0 up to Month 50, according to the MedDRA classification.
- The occurrence of seizures within 30 days (day of vaccination and 29 subsequent days) after each dose of study vaccine, according to the MedDRA classification.
- The occurrence of generalized convulsive seizure within seven days (day of vaccination and six subsequent days) after each dose of study vaccine, according to the Brighton collaboration guidelines [Bonhoeffer, 2004].
- The occurrence of unsolicited AEs within 30 days (day of vaccination and 29 subsequent days) after each dose of study vaccine, according to the MedDRA classification.
- The concentration of biochemistry (ALT, creatinine) and hematology (hemoglobin, WBC, platelets) parameters in the first 50 subjects (25 subjects per site) enrolled in each group (reactogenicity sub-cohort) before Dose 3, seven days post-Dose 3 and 30 days post-Dose 3.

- **Reactogenicity (reactogenicity sub-cohort)**

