9.1. Safety definitions

9.1.1. Definition of an adverse event

An AE is any untoward medical occurrence in a clinical investigation subject, temporally associated with the use of a medicinal product, whether or not considered related to the medicinal product.

An AE can therefore be any unfavorable and unintended sign (including an abnormal laboratory finding), symptom, or disease (new or exacerbated) temporally associated with the use of a medicinal product. For marketed medicinal products, this also includes failure to produce expected benefits (i.e. lack of efficacy), abuse or misuse.

Examples of an AE include:

- Significant or unexpected worsening or exacerbation of the condition/indication under study.
- Exacerbation of a chronic or intermittent pre-existing condition including either an increase in frequency and/or intensity of the condition.
- New conditions detected or diagnosed after investigational vaccines administration even though they may have been present prior to the start of the study.
- Signs, symptoms, or the clinical sequelae of a suspected interaction.
- Signs, symptoms, or the clinical sequelae of a suspected overdose of either investigational vaccines or a concurrent medication (overdose per se should not be reported as an AE/SAE).
- Signs, symptoms temporally associated with vaccines administration.
- Significant failure of expected pharmacological or biological action.
- Pre- or post-treatment events that occur as a result of protocol-mandated procedures (i.e. invasive procedures, modification of subject's previous therapeutic regimen).

AEs to be recorded as endpoints (solicited AEs) are described in Section 9.1.3. All other AEs will be recorded as UNSOLICITED AEs.

Examples of an AE DO NOT include:

- Medical or surgical procedures (e.g. endoscopy, appendectomy); the condition that leads to the procedure is an AE/SAE.
- Situations where an untoward medical occurrence did not occur (e.g. social and/or convenience admission to a hospital, admission for routine examination).
- Anticipated day-to-day fluctuations of pre-existing disease(s) or condition(s) present or detected at the start of the study that do not worsen.
- Pre-existing conditions or signs and/or symptoms present in a subject prior to the first study vaccination. These events will be recorded in the medical history section of the eCRF.

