9.1.2. Definition of a serious adverse event

A SAE is any untoward medical occurrence that:

- a. Results in death,
- b. Is life-threatening,

Note: The term 'life-threatening' in the definition of 'serious' refers to an event in which the subject was at risk of death at the time of the event. It does not refer to an event, which hypothetically might have caused death, had it been more severe.

- c. Requires hospitalization or prolongation of existing hospitalization,

Note: In general, hospitalization signifies that the subject has been admitted at the hospital or emergency ward for observation and/or treatment that would not have been appropriate in the physician's office or in an out-patient setting. Complications that occur during hospitalization are also considered AEs. If a complication prolongs hospitalization or fulfills any other serious criteria, the event will also be considered serious. When in doubt as to whether 'hospitalization' occurred or was necessary, the AE should be considered serious.

Hospitalization for elective treatment of a pre-existing condition (known or diagnosed prior to informed consent signature) that did not worsen from baseline is NOT considered an AE.

- d. Results in disability/incapacity.

Note: The term disability means a substantial disruption of a person's ability to conduct normal life functions. This definition is not intended to include experiences of relatively minor medical significance such as uncomplicated headache, nausea, vomiting, diarrhea, influenza like illness, and accidental trauma (e.g. sprained ankle) which may interfere or prevent everyday life functions but do not constitute a substantial disruption.

Medical or scientific judgement should be exercised in deciding whether reporting is appropriate in other situations, such as important medical events that may not be immediately life-threatening or result in death or hospitalization but may jeopardize the subject or may require medical or surgical intervention to prevent one of the other outcomes listed in the above definition. These should also be considered serious. Examples of such events are invasive or malignant cancers, intensive treatment in an emergency room or at home for allergic bronchospasm, blood dyscrasias or convulsions that do not result in hospitalization.

In this study, the AEs of specific interest (i.e. pIMDs, meningitis and seizure within 30 post-vaccination) will be reported as SAEs.

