All cases of severe malaria and cerebral malaria will be reported as SAEs and clinical details of each case will be reported in a specific eCRF screen (refer to Section 9.1.5).

9.1.3. **Solicited adverse events**

9.1.3.1. **Solicited local (injection-site) adverse events**

The following local (injection-site) AEs will be solicited:

Table 24 Solicited local adverse events

All age groups
Pain at injection site
Redness* at injection site
Swelling at injection site

* In case the principal investigator or designate is unable to determine the extent of redness on darkly pigmented skin, it will be reported as uninterpretable in the eCRF

9.1.3.2. **Solicited general adverse events**

The following general AEs will be solicited:

Table 25 Solicited general adverse events

Infant/Toddler/Child (< 6 years)
Drowsiness
Fever
Irritability/Fussiness
Loss of appetite

Note: Temperature will be recorded daily. Should additional temperature measurements be performed at other times of day, the highest temperature will be recorded in the eCRF.

9.1.4. Clinical laboratory parameters and other abnormal assessments qualifying as adverse events or serious adverse events

In absence of diagnosis, abnormal laboratory findings (e.g. clinical chemistry, hematology, urinalysis) or other abnormal assessments (e.g. failure to thrive) that are judged by the investigator to be clinically significant will be recorded as AE or SAE if they meet the definition of an AE or SAE (refer to Sections 9.1.1 and 9.1.2). Clinically significant abnormal laboratory findings or other abnormal assessments that are present at baseline and significantly worsen following the start of the study will also be reported as AEs or SAEs.

The investigator will exercise his or her medical and scientific judgement in deciding whether an abnormal laboratory finding or other abnormal assessment is clinically significant.

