7.5. Analysis of safety and reactogenicity

7.5.1. Analysis of safety and reactogenicity planned in the protocol

The primary analysis of safety will be based on the ES. Analyses containing only solicited data will be based on the solicited safety set.

Among the reactogenicity sub-cohort (first 50 subjects enrolled in each group) the percentage of subjects with at least one local AE (solicited and unsolicited), with at least one general AE (solicited and unsolicited) and with any AE during the solicited follow-up period (i.e. four days post-Dose 3, Dose 4, Dose 5 and Dose 6) will be tabulated with exact 95% CI after each vaccine dose and overall. The percentage of doses followed by at least one local AE (solicited and unsolicited), by at least one general AE (solicited and unsolicited) and by any AE will be tabulated for the whole solicited follow-up period (i.e. four days post-Dose 3, Dose 4, Dose 5 and Dose 6), with exact 95% CI. Similar tables will be generated for Grade 3 AEs and AEs considered as causally related to vaccination.

Among the reactogenicity sub-cohort (first 50 subjects enrolled in each group), the percentage of subjects reporting each individual solicited local and general AE during the solicited follow-up period (i.e. four days post-Dose 3, Dose 4, Dose 5 and Dose 6) will be tabulated with exact 95% CI. The percentage of doses followed by each individual solicited local and general AE will be tabulated for each dose and for the whole solicited follow-up period (i.e. four days post-Dose 3, Dose 4, Dose 5 and Dose 6), with exact 95% CI. Similar tables will be generated for Grade 3 AEs, causal events and for fever, temperature in 0.5°C increments.

The verbatim reports of unsolicited symptoms will be reviewed by a physician and the signs and symptoms will be coded according to the MedDRA. The percentage of subjects with at least one report of an unsolicited AE classified by the MedDRA preferred term level, occurring within 30 days (day of vaccination and 29 subsequent days) after each dose of study vaccine will be tabulated with exact 95% CI.

204889 (Malaria-094) Statistical Analysis Plan

The percentage of subjects reporting an SAE (all, fatal, related) occurring within 30 days (day of vaccination and 29 subsequent days) after each dose of study vaccine, classified by the MedDRA preferred term level will be tabulated with exact 95% CI.

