The percentage of subjects reporting an SAE (all, fatal, related) from Dose 1 (Day 0) until Month 14, from Day 0 until Month 21, from Day 0 until Month 26, from Day 0 until Month 33 and over the whole study duration (Dose 1 [Day 0] until Month 50), classified by the MedDRA preferred term level, will be tabulated with exact 95% CI.

The percentage of subjects reporting an AE or SAE leading to withdrawal from further vaccination from Dose 1 (Day 0) until Month 50, classified by the MedDRA preferred term level, will be tabulated with exact 95% CI.

The percentage of subjects reporting severe malaria cases and cerebral malaria cases from Day 0 up to Month 14, Day 0 up to Month 21, Day 0 up to Month 26, Day 0 up to Month 33 and Day 0 up to Month 50 and over successive years within the study will be tabulated with exact 95% CI.

The percentage of subjects reporting pIMDs from Day 0 up to Month 14, Day 0 up to Month 21, Day 0 up to Month 26, Day 0 up to Month 33 and Day 0 up to Month 50, classified by the MedDRA preferred term level will be tabulated with exact 95% CI.

The percentage of subjects reporting meningitis from Day 0 up to Month 14, Day 0 up to Month 20, Day 0 up to Month 26, Day 0 up to Month 32 and Day 0 up to Month 50 classified by the MedDRA preferred term level will be tabulated with exact 95% CI.

The percentage of subjects reporting seizures occurring within 30 days (day of vaccination and 29 subsequent days) after each dose of study vaccine, classified by the MedDRA preferred term level will be tabulated with exact 95% CI.

For generalized convulsive seizures occurring within seven days following a dose of study vaccine, an analysis will be performed based on the Brighton Collaboration guidelines [Bonhoeffer, 2004]. This includes descriptive tables of the time relationship of seizures to vaccination, the duration of seizures and the level of diagnostic certainty.

Biochemistry (ALT, creatinine) and hematology (hemoglobin, WBC, platelets) values that are outside of the reference ranges (see protocol section 7.5.2.1) will be described for the reactogenicity sub-cohort (first 50 subjects enrolled in each group) before Dose 3, seven days post-Dose 3 and 30 days post-Dose 3. Frequency distribution of results by toxicity grades will be tabulated by group.

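### The SAE totals are planned only with malaria included, so a diffuse excess of non-malaria SAEs over Control could go unseen

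*Protocol*

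**What the plan says.** The endpoint in the synopsis and in Protocol 11.2 is "The occurrence of SAEs (all, fatal and related) during the whole study period according to the MedDRA classification". SAP 7.5.1 plans "The percentage of subjects reporting an SAE (all, fatal, related) from Dose 1 (Day 0) until Month 14", and the same from Day 0 to Months 21, 26, 33 and 50, classified by MedDRA preferred term with exact 95% CIs. Protocol 11.10 has the Month 14, Month 26 and Month 50 windows.

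Malaria enters these counts by two routes in Protocol 9.1.2. The first is explicit: "All cases of severe malaria and cerebral malaria will be reported as SAEs and clinical details of each case" go to a dedicated eCRF screen. The second is the general criterion "Requires hospitalization or prolongation of existing hospitalization", which has no exception for malaria.

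Separate tables are planned for severe and cerebral malaria, potential immune-mediated diseases, meningitis and seizures (SAP 7.5.1). Severe and cerebral malaria cases are also listed (SAP 7.5.2.3). Neither document describes an SAE total without malaria, and SAP 10, which records changes from the protocol, adds none.

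**The concern.** The trial's premise is that RTS,S lowers malaria incidence. The percentage of children with any SAE is therefore expected to differ from Control for a reason unrelated to harm. If non-malaria SAEs are more common under RTS,S, the malaria SAEs prevented offset them in the total.

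The preferred-term rows do not undo this. One child can appear under several terms, so the share with at least one non-malaria SAE is neither the sum of the rows nor the total minus the malaria row. As a hypothetical case, three non-malaria terms at 5% each fit any share from 5% (the same children each time) to 15% (different children).

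At stake is the broadest safety contrast that runs concurrently with Control in every group from Day 0 to Month 50. The fatal-SAE total has the same structure.

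**Working it through.** The documents give no SAE rate, detectable excess or safety power, so there is no planned figure to reproduce. The check asks how large a non-malaria excess would leave the all-SAE total exactly equal to Control.

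**Inputs**
- Control incidence λ = 0.5 episodes per person-year (Protocol 11.4, where it is a minimum).
- Follow-up T = 50/12 = 4.17 years, so λT = 2.083.
- Efficacy VE = 36.3%: all clinical episodes over 48 months, with a fourth dose (Protocol 1.1 and 1.3.2). Applying it to malaria SAEs is an assumption.
- Share of episodes hospitalised, h: not in the documents; 1%, 2%, 5% and 10% are tried.
- Non-malaria SAE risk in Control, q = 15%: assumed, and taken as independent of malaria.

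**Formulas**
- Malaria-SAE risk: m_C = 1 − exp(−λTh) in Control; m_V = 1 − exp(−λTh(1 − VE)) in RTS,S.
- Control total: 1 − (1 − m_C)(1 − q).
- RTS,S non-malaria risk that gives the same total: q′ = 1 − (1 − m_C)(1 − q)/(1 − m_V) = 1 − (1 − q)exp(−λTh·VE).

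**Worked line, h = 5%**
- λTh = 0.1042, so m_C = 9.9%.
- 0.1042 × 0.637 = 0.0664, so m_V = 6.4%.
- Control total = 1 − 0.901 × 0.85 = 23.4%.
- q′ = 1 − 0.85 × exp(−0.0378) = 18.2%, which is 3.2 points above 15%, a relative risk of 1.21.

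| h | m_C | m_V | Control total | q′ | Excess cancelled | Relative risk cancelled |
|---|---|---|---|---|---|---|
| 1% | 2.1% | 1.3% | 16.7% | 15.6% | 0.6 points | 1.04 |
| 2% | 4.1% | 2.6% | 18.5% | 16.3% | 1.3 points | 1.09 |
| 5% | 9.9% | 6.4% | 23.4% | 18.2% | 3.2 points | 1.21 |
| 10% | 18.8% | 12.4% | 31.0% | 21.2% | 6.2 points | 1.41 |

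**Sensitivity to efficacy**

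The protocol also gives 28.3% (48 months, no fourth dose) and 55.1% (12 months post-Dose 3). From the last form of q′:
- VE 28.3%: cancelled relative risk 1.03, 1.07, 1.16 and 1.32 for the four values of h.
- VE 55.1%: 1.06, 1.13, 1.32 and 1.61.

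**Check with a simpler model**

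Set the Control malaria-SAE risk m directly and let RTS,S reduce it to m(1 − VE). With m = 10%, q = 10% and VE = 36.3%:
- q′ = 1 − 0.90 × 0.90/(1 − 0.0637) = 13.5%, a cancelled relative risk of 1.35.
- If the true non-malaria relative risk were 1.3, the totals would be 19.0% in Control and 1 − 0.9363 × 0.87 = 18.5% in RTS,S. The excess would read as a slight benefit.

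Over m from 2% to 15%, q from 5% to 20% and the three efficacy values, the cancelled relative risk runs from 1.02 to 2.68.

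**The case against.** The case against has four parts.

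**The total carries no decision.** Safety is summarised by group, with no between-group test, risk difference or decision rule, and SAP 8 treats the remaining secondary endpoints as descriptive. This stands. A reader might infer lost power from a power calculation on the totals, but no safety test is planned, and neither is pooling the four RTS,S groups against Control, so power is not the measure of this point.

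**Much is visible elsewhere.** Malaria has its own preferred-term rows, as does every other term, and the named safety signals have their own tables. A reader might infer that any real non-malaria excess would be hidden. The documents do not support that: an excess in one term or one named signal would show. Only an excess spread over many terms can hide.

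**Size and direction are uncertain.** The hospitalised share and the 15% are assumptions, and at 1% to 2% hospitalised the effect is small. A reader might also infer that the total always favours the vaccine. Protocol 1.3.1 lists a delayed increase in severe malaria as an important potential risk, seen in the Phase III study in children without a fourth dose. The malaria component could therefore also inflate the RTS,S total. That is a further reason to show the components separately.

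**The table list is held outside the SAP.** SAP 11.2 places it in the trial master file, so a malaria-excluded row may exist there. The supplied text does not commit to one.

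A reader might extend the point to unsolicited AEs, since the 30-day summaries also include malaria. That extension is not made. Control is dosed only at Months 0, 1 and 2, so the later post-dose windows have no concurrent Control window, and no size has been worked out.

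**Conclusion.** The point holds for the all-SAE and fatal-SAE totals. As described, they combine malaria SAEs prevented with any non-malaria SAEs caused, and nothing else planned gives the share of children with at least one non-malaria SAE. Under the stated assumptions the non-malaria relative risk that disappears from the all-SAE total is about 1.04 to 1.41. The result depends mainly on how often malaria leads to hospitalisation, on the non-malaria background, and on whether efficacy against clinical episodes carries over to malaria SAEs. No size is given for fatal SAEs. The loss is of a readable contrast with Control. It invalidates no planned test and gives no evidence that such an excess exists. It is worth correcting because the correction is cheap.

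**What to change.** In SAP 7.5.1, add to each cumulative SAE table (Day 0 to Months 14, 21, 26, 33 and 50) a row for children with at least one SAE excluding malaria preferred terms. Give it for all SAEs and for fatal SAEs, by group, with exact 95% CIs. Make the matching change in Protocol 11.10. Keep the existing all-SAE and fatal-SAE rows beside it, so that any delayed severe malaria stays in view. Fix the list of malaria preferred terms before database lock; the trial is open-label, and a list chosen later would be open to question. A descriptive risk difference versus Control is optional.

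The cost is two rows per cumulative table and a short term list, with no new data, visit or sample. One limitation should be stated with the row: malaria can predispose to other illness, so the malaria-excluded figure is not entirely free of the efficacy effect.

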eTDF:	Electronic temperature excursion decision form
EU/ml:	ELISA unit per milliliter
FDA:	Food and Drug Administration, United States of America
Fx:	Fractional
Fx017M:	Group of subjects enrolled in study MALARIA-071, who were randomized to receive two full doses of RTS,S/AS01 _B at Month 0 and Month 1 and a third fractional dose (1/5 th dose) at Month 7.
g/dl:	Gram per deciliter
GCP:	Good Clinical Practice
GMC:	Geometric mean concentration
GSK:	GlaxoSmithKline
HDCV:	Human diploid cells vaccine
HIV:	Human immunodeficiency virus
ICF:	Informed consent form
ICH:	International Committee on Harmonization
IDMC:	Independent Data Monitoring Committee
IEC:	Independent Ethics Committee
IgG:	Immunoglobulin G
IM:	Intramuscular
IMP:	Investigational medicinal product
IRB:	Institutional Review Board
ITN:	Insecticide-treated bednet

IU/ml:	International unit per milliliter
KEMRI/USAMRU-K, WRP:	Kenya Medical Research Institute / US Army Medical Research Unit Kenya, Walter Reed Project
LAR:	Legally acceptable representative
MATEX:	MATerial EXcellence
MedDRA:	Medical dictionary for regulatory activities
mEq/l:	Milliequivalents per liter
mg/dl:	Milligram per deciliter
mIU/ml:	Milli-international unit per milliliter
mmol/l:	Millimole per liter
MPL:	3-O-desacyl-4'-monophosphoryl lipid A (produced by GSK)
PBS:	Phosphate buffered saline
PCD:	Passive case detection
PCECV:	Purified chick embryo cells vaccine
PCR:	Polymerase chain reaction
PDEV:	Purified duck embryo cells vaccine
P. falciparum:	Plasmodium falciparum
PHKCV:	Purified hamster kidney cells vaccine
pIMD:	Potential immune-mediated disease
POC:	Proof of concept
PT:	Preferred term
PVRV:	Purified Vero cell rabies vaccine
Pyr:	Person year at risk
QS-21:	Quillaja saponaria Molina , fraction 21 (Licensed by GSK from Antigenics Inc., a wholly owned subsidiary of Agenus Inc., a Delaware, USA corporation)
RDT:	Rapid diagnostic test

RTS,S:	Particulate antigen, containing both RTS and S (hepatitis B surface antigen) proteins
RTS,S/AS01E:	GSK Biologicals' candidate Plasmodium falciparum malaria vaccine adjuvanted with GSK Biologicals' proprietary Adjuvant System AS01 _E
SAE:	Serious adverse event
SAS:	Statistical Analysis System
SBIR:	Randomization System on Internet
SCR:	Screening
SD:	Standard deviation
SDV:	Source document verification
SmPC:	Summary of product characteristics
SPM:	Study procedures manual
TVC:	Total vaccinated cohort
UNAIDS:	Joint United Nations Programme on HIV/AIDS
USA:	United States of America
Vacc:	Vaccination
VNA:	Virus neutralizing antibody
WBC:	White blood cells
WHO:	World Health Organization

Amended 14 November 2019

GLOSSARY OF TERMS

Adverse event:	Any untoward medical occurrence in a patient or clinical investigation subject, temporally associated with the use of a medicinal product, whether or not considered related to the medicinal product.
	An adverse event (AE) can therefore be any unfavorable and unintended sign (including an abnormal laboratory finding), symptom, or disease (new or exacerbated) temporally associated with the use of a medicinal product. For marketed medicinal products, this also includes failure to produce expected benefits (i.e. lack of efficacy), abuse or misuse.
Active detection of infection:	Detection of a malaria infection by the regular examination of each subject for malaria parasitemia i.e. regardless of whether the subject had signs or symptoms of infection.
Blinding:	A procedure in which one or more parties to the trial are kept unaware of the treatment assignment in order to reduce the risk of biased study outcomes. The level of blinding is maintained throughout the conduct of the trial, and only when the data are cleaned to an acceptable level of quality will appropriate personnel be unblinded or when required in case of a serious adverse event. In an open-label study, no blind is used. Both the investigator and the subject know the identity of the treatment assigned.
Child in care:	A child who has been placed under the control or protection of an agency, organization, institution or entity by the courts, the government or a government body, acting in accordance with powers conferred on them by law or regulation. The definition of a child in care can include a child cared for by foster parents or living in a care home or institution, provided that the arrangement falls within the definition above. The definition of a child in care does not include a child who is adopted or has an appointed legal guardian.
Comparator vaccine:	In this study, the comparator vaccine is a non-malaria vaccine (rabies vaccine) administered to subjects randomized in the Control group.

Compound:

A cluster of buildings in an enclosure, such as the houses of an extended family. The enclosure may be a wall, a fence, a hedge or some other structure, or it may be formed by the buildings themselves, when they are built around an open area or joined together.

Control group:

A concurrent control group is one chosen from the same population as the test group and treated in a defined way as part of the same trial that studies the test treatment, and over the same period of time. The test and control groups should be similar with regard to all baselines and on treatment variables that could influence outcome, except for the study treatment [ICH E10, 2000].

In this study the Control group will receive a non-malaria comparator vaccine (rabies vaccine).

Electronic case report form:

Auditable electronic record designed to capture information required by the clinical trial protocol to be reported to the sponsor on each trial subject.

Eligible:

Qualified for enrolment into the study based upon strict adherence to inclusion/exclusion criteria.

End of Study (EoS):

(Synonym of End of Trial)

For studies without collection of human biologicals samples or imaging data EoS is the Last Subject Last Visit (LSLV).

For studies with collection of Human Biologicals Samples or imaging data, EoS is defined as the date of the last testing/reading released of the Human Biologicals Samples or imaging data, related to primary and secondary endpoints. EoS must be achieved no later than 8 months after LSLV.

Epoch:

An epoch is a self-contained set of consecutive timepoints or a single timepoint from a single protocol. Self-contained means that data collected for all subjects at all timepoints within that epoch allows to draw a complete conclusion to define or precise the targeted label of the product. Typical examples of epochs are primary vaccinations, boosters, yearly immunogenicity follow-ups, and surveillance periods for efficacy or safety.

eTrack:

GSK's tracking tool for clinical trials.

Evaluable:	Meeting all eligibility criteria, complying with the procedures defined in the protocol, and, therefore, included in the according-to-protocol (ATP) analysis (see Sections 7.7.2 and 11.5 for details on criteria for evaluability).
Immunological correlate of protection:	The defined immune response above which there is a high likelihood of protection in the absence of any host factors that might increase susceptibility to the infectious agent.
Investigational vaccine: (Synonym of Investigational Medicinal Product)	A pharmaceutical form of an active ingredient or placebo being tested or used as a reference in a clinical trial, including a product with a marketing authorization when used in a way different from the approved form, or when used for an unapproved indication, or when used to gain further information about an approved use.
Legally acceptable representative: (The terms legal representative or legally authorized representative are used in some settings.)	An individual or juridical or other body authorized under applicable law to consent, on behalf of a prospective subject, to the subject's participation in the clinical trial.
Potential immune-mediated disease:	Potential immune-mediated diseases (pIMDs) are a subset of AEs that include autoimmune diseases and other inflammatory and/or neurologic disorders of interest which may or may not have an autoimmune etiology.
Passive case detection:	Detection of malaria disease by self-presentation to health facility in the study area. If there is a history of fever within 24 hours or axillary temperature is $\geq 37.5^{\circ}\text{C}$ at presentation then a blood slide is taken and examined for parasitemia.
Primary completion date:	The date that the final subject was examined or received an intervention for the purpose of final collection of data for the primary outcome, whether the clinical trial concluded according to the pre-specified protocol or was terminated.
Protocol amendment:	The International Conference on Harmonization (ICH) defines a protocol amendment as: 'A written description of a change(s) to or formal clarification of a protocol.' GSK Biologics further details this to include a change to an approved protocol that affects the safety of subjects,

scope of the investigation, study design, or scientific integrity of the study.

Protocol administrative change: A protocol administrative change addresses changes to only logistical or administrative aspects of the study.

Randomization: Process of random attribution of treatment to subjects in order to reduce bias of selection.

Self-contained study: Study with objectives not linked to the data of another study.

Site monitor: An individual assigned by the sponsor who is responsible for assuring proper conduct of clinical studies at one or more investigational sites.

Serious adverse event: A serious adverse event (SAE) is any untoward medical occurrence that:

- a. results in death;
- b. is life-threatening;
- c. requires hospitalization or prolongation of existing hospitalization;
- d. results in disability/incapacity.

Medical or scientific judgment should be exercised in deciding whether reporting is appropriate in other situations, such as important medical events that may not be immediately life-threatening or result in death or hospitalization but may jeopardize the subject or may require medical or surgical intervention to prevent one of the other outcomes listed in the above definition. These should also be considered serious. Examples of such events are invasive or malignant cancers, intensive treatment in an emergency room or at home for allergic bronchospasm or blood dyscrasias or convulsions that do not result in hospitalization.

In this study, the AEs of specific interest (i.e. pIMDs, meningitis and seizure within 30 post-vaccination) will be reported as SAEs.

Solicited adverse event: AEs to be recorded as endpoints in the clinical study. The presence/occurrence/intensity of these events is actively solicited from the subject or an observer during a specified post-vaccination follow-up period.

Sub-cohort:	A group of subjects for whom specific study procedures are planned as compared to other subjects.
Subject:	Term used throughout the protocol to denote an individual who has been contacted in order to participate or participates in the clinical study, either as a recipient of the vaccine or as a control.
Subject number:	A unique number identifying a subject, assigned to each subject consenting to participate in the study.
Subset:	A group of subjects who have the same biological samples taken at the same timepoint, but the assay to be performed on that biological sample will be different.
Treatment:	Term used throughout the clinical study to denote a set of investigational product(s) or marketed product(s) or placebo intended to be administered to a subject, identified by a unique number, according to the study randomization or treatment allocation.
Treatment number:	A number identifying a treatment to a subject, according to the study randomization or treatment allocation.
Unsolicited adverse event:	Any AE reported in addition to those solicited during the clinical study. Also any 'solicited' symptom with onset outside the specified period of follow-up for solicited symptoms will be reported as an unsolicited adverse event.

Amended 14 November 2019

TRADEMARKS

The following trademarks are used in the present protocol.

Note: In the body of the protocol (including the synopsis), the names of the vaccines/products will be written without the superscript symbol TM or [®] and in *italics*.

Trademark of the GlaxoSmithKline group of companies	Generic description
Rabipur TM	Purified chick embryo cell culture rabies vaccine

Amended 14 November 2019

